Once approved for participation in the study all participants will undergo a brief instructional class on how to operate the HMD and will be allowed sufficient time to become comfortable with its use. We expect approximately 5-10 minutes to be required for this portion of the study. Once familiar with the use of the VR headset, participants will be asked to randomly draw an envelope from a container. This envelope will contain a block and sequence number. The block and sequence number will be the subject ID and will correspond to a predetermined number set on a separate document that will determine if the participant will use the HMD during venipuncture or not. The screener will not have immediate access to the list showing which group the participant will be assigned to. One member of the study team will be present in the lab room to ensure the participant uses the VR headset (or not) according to what is randomly drawn. This member of the research team will have the list showing whether or not the participant is assigned to the control arm or the experimental arm. The participants will then proceed to the specimen room to undergo venipuncture.

Venipuncture for both groups will occur in the non-dominant arm. The reasoning for this is that the Oculus Go requires one free hand to use a controller. This will ensure that the individuals participating are able to effectively use the device. Those unable to undergo venipuncture in the non-

dominant arm will undergo venipuncture in the dominant arm instead and will use the Oculus Go controller with their non-dominant hand.

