Those utilizing the Oculus Go HMD will be interacting with the VR game Ocean Rift. They will utilize a single controller to explore an underwater safari park. Ocean Rift has multiple environments to choose from, including coral reefs, ship wrecks, lagoons, the arctic, and prehistoric seas. Participants may interact with and learn about different creatures to include dolphins, turtles, orcas, ray, whales, sea lions, manatees, and dinosaurs. During the game users may travel where they please and interact with what they choose. The VR device is equipped with head-tracking software that allows the user to choose direction by looking around. The entire interior and exterior of the headset will be cleaned with alcohol-based wipes after each use. Alcohol will be used since it is generally well-tolerated on human skin, and since it evaporates quickly. The headset will be dried in the open air for a minimum of two minutes between each subject's use.

Those not using the VR will still wear a headset that will simply be turned off. This is to ensure that any significant change noted with the VR is due to the use of VR itself, and not simply due to "blindfolding" the patient during the procedure.

As some patients experiencing anxiety may be tempted to move during the procedure, lab personnel will instruct participants to remain still during venipuncture. Participants will be advised that they may take breaks as needed if anxiety becomes overwhelming.

After undergoing the procedure, each participant will be asked to fill out the post-procedure questionnaire and return it to the study team member present in the lab room, who will clean the headset as the participant completes the questionnaire. This questionnaire assesses the patient's pain intensity and level of anxiety with the VAS similar to the VAS shown above, as well as the patient's satisfaction with the visit which will be measured utilizing a Likert scale for individual questions (see below).

Overall, how satisfied were you with the use of Virtual Reality in reducing your pain level?

5 Very Satisfied	4 Satisfied	3 Not Sure	2 Unsatisfied	1 Very Unsatisfied
---------------------	----------------	---------------	------------------	-----------------------

Overall, how satisfied were you with the use of Virtual Reality in reducing your anxiety level?

5 Very Satisfied	4 Satisfied	3 Not Sure	2 Unsatisfied	1 Very Unsatisfied

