13.0 Recruitment and Consent

13.1 Please describe the recruitment process, including how subjects will be identified and selected for the study.

When approaching the ticket stand to draw a waiting number for the lab, prospective participants will be asked by an assistant investigator located near the kiosk if they are interested in participating in the study. Participants will be selected in consecutive order (as long as the screening room is open) to avoid selection bias. However, patients who are obviously outside of the age range of 18-50 will not be asked to participate, although this process may leave room for some selection bias. If participants express desire, they will move to a screening station located in a private room near the lab to be educated on the details of the study, to include any risks. If they consent, they will fill out a screening questionnaire. If patients are eligible, they'll be given a brief tutorial on use of the VR headset and randomly assigned an envelope containing a card stating that they will use VR during venipuncture or undergo standard practice (the researcher will be blind to which group the participant is assigned to). Once instruction is complete, they'll return to the lab waiting area to draw a ticket to provide a specimen IAW standard lab practice.

13.2 Compensation for Participation:

There will not be any compensation (payment or otherwise) for participating in this study.

13.3 Please describe the pre-screening process. If no pre-screening, enter Not Applicable in the text editor

When patients approach the ticket kiosk, a member of the study team will ask them if they're interested in participating in a study related to pain control with venipuncture. To avoid perceived coercion, the recruiter will be in scrubs so that his rank will not be visible. If the participants wish to participate, they'll be directed to a screening station in a private room.

At the screening station, candidates will be screened to insure they meet inclusion/exclusion criteria by completing a prescreening form that addresses all participation criteria. After that, they'll be provided informed consent documents and will undergo a brief tutorial for use of the VR headset prior to returning to the lab waiting area to draw a ticket.

13.4 Consent Process:

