possession of the PI. When not in the PI's possession it will be secured in a locked office. The de-identified electronic data will be stored on the attached Excel spreadsheet. Paper copies will be shredded once data has been transferred. Once the study is complete the electronic documents will be maintained on the primary investigator's CAC-enabled/password protected government computer until the computer is turned in upon PCSing and then deleted.

14.4 Potential Benefits:

Describe any real and potential benefits of the research to the subject and any potential benefits to a specific community or society

If the individuals in the research are considered experimental subjects (per 10 USC 980), and they cannot provide their own consent, the protocol must describe the intent to directly benefit all subjects

The subjects in the experimental group will potentially benefit from this study via reduction in anxiety and pain control, but will not directly benefit from this study in any other way. If Virtual Reality is shown to decrease pain intensity and anxiety levels with venipuncture, it may be offered in the lab setting, clinic setting, emergency room setting, or deployed setting to improve the care that can be provided.

14.5 Privacy for Subjects:

Describe the measures to protect subject's privacy during recruitment, the consent process, and all research activities, etc.

During the screening process no PHI will be collected. The participant's name and signature will be on the consent form, but will not be linked to any PHI. The screening questionnaire will contain age and gender, and will ask several questions about health, but will not be linked to the consent form and therefore will not contain PHI. This will be performed in a private room with only the member of the study team collecting the data present. Once gathered, the data will be stored in electronic form on a secure CAC-enabled/password protected government computer that will be in the possession of the PI. After paper documents are transferred electronically they will be shredded, the electronic documents will be kept for 3 years and then deleted.

14.6 Incidental or Unexpected Findings:

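### The switched-off headset rules out blindfolding, but not expectation in unblinded participants who rate their own pain, so Section 10.1 cannot attribute any difference to VR itself

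*Combined protocol and SAP*

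**What the plan says.** Section 10.1 describes the two conditions. In the experimental arm, "Those utilizing the Oculus Go HMD will be interacting with the VR game Ocean Rift". In the control arm, "Those not using the VR will still wear a headset that will simply be turned off". The reason follows: "This is to ensure that any significant change noted with the VR is due to the use of VR itself", and the sentence ends "and not simply due to 'blindfolding' the patient during the procedure".

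Before allocation, Section 10.1 says that "all participants will undergo a brief instructional class on how to operate the HMD", with an expected 5 to 10 minutes for this step. The envelope is drawn after it.

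The plan describes the envelope in two ways. Section 10.1 says it holds a block and sequence number, which is matched to a list held by the team member in the lab room. Section 13.1 describes an envelope "containing a card stating that they will use VR during venipuncture or undergo standard practice". The only blinding mentioned is of the researcher, in 13.1. No section describes blinding of participants.

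The primary outcome (11.1) is the participant's own mark on a 100 mm pain VAS after the procedure, compared between arms by a t-test (11.1, 11.6). Expected pain is also rated on a VAS, but on the screening questionnaire, before allocation (10.1).

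**The concern.** The sentence in 10.1 has two parts. The second, that a difference would not be simply blindfolding, is sound. The first makes a wider causal claim: that the control ensures any significant change comes from VR itself. Excluding one rival explanation does not exclude the others.

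The main remaining rival is expectation. Participants have just tried the headset. Those given the game may expect less pain, and those given a dark headset may be disappointed. Either reaction can move a self-rated pain score, and both would widen the difference in favour of VR.

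What is at stake is the conclusion. Section 9.2 foresees strong implications for emergency department use if a significant difference is found, and 14.4 foresees offering VR in several care settings if it is shown to reduce pain and anxiety. The plan nowhere states that participants are unblinded and rate their own outcome, and no planned variable would describe expectation once the arm is known.

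**Working it through.** **1. What the control equalises.**

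| Explanation for a difference | Same in both arms? | Basis |
|---|---|---|
| Covering the eyes | Yes | 10.1: both arms wear a headset |
| Wearing the device | Yes | 10.1 |
| Knowing which condition was received | No | 10.1: interactive game against dark display, after both arms were taught to use the headset |
| Expectation or disappointment | No | Follows from the row above |
| Effect of these on the outcome | Not excluded | 11.1: the participant's own VAS mark |

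The arm becomes known under either description of the envelope. Under 13.1 the card states it. Under 10.1 it is revealed in the lab room at the latest, when the display is seen to be on or off. Both come before the needle.

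The expected-pain VAS cannot settle the matter. It is completed before allocation, so it cannot record expectation created by the arm, and adjusting for it would not remove the problem.

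**2. The plan's own sample size.** Inputs from 11.5: difference 13 mm, SD 17 mm, two-sided alpha 0.05, power 0.80.

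n per arm = 2 × (1.960 + 0.842)² × (17/13)² = 26.8, rounded up to 27. Total 54, and 54/0.90 = 60. The plan's figures reproduce. (The exact t-based value is 27.8, so 28; nothing here depends on it.)

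**3. Illustration of size.** The documents give no figure for an expectation effect, so the shift is assumed. The SD is the protocol's 17 mm.

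- Standard error, 30 per arm: 17 × √(2/30) = 4.39 mm.
- Smallest significant difference: 2.002 × 4.39 = 8.8 mm (58 degrees of freedom).
- With no effect of VR and a shift b, the chance of p<0.05 comes from the noncentral t with noncentrality b/4.39.
- The chance that the observed difference is 13 mm or more is 1 − Φ((13 − b)/4.39).

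| Assumed shift b | Noncentrality | Chance of p<0.05 | Chance of observed ≥13 mm |
|---|---|---|---|
| 0 mm | 0 | 5% | 0.2% |
| 3 mm | 0.68 | 10% | 1.1% |
| 4 mm | 0.91 | 15% | 2.0% |
| 5 mm | 1.14 | 20% | 3.4% |

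At 27 per arm the standard error is 4.63 mm and the smallest significant difference 9.3 mm. Shifts of 3, 4 and 5 mm then give 10%, 14% and 19% for p<0.05. At 3 and 5 mm the chance of 13 mm or more is 1.5% and 4.2%.

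The results depend on the assumed shift. At 8 or 10 mm with 30 per arm, the chance of p<0.05 would be 43% or 61%, and of 13 mm or more 13% or 25%. The documents do not say which shift is realistic.

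**The case against.** The best defence has four parts.

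- **The sentence was aimed at blindfolding.** Read to its end, it names occlusion as the explanation to be removed, and the switched-off headset removes it. This stands, and the control deserves credit for it. What remains is that ensuring an effect of VR itself goes beyond that purpose.
- **The total effect may be what matters.** The plan compares standard practice with standard practice plus VR (9.4), and someone deciding whether to offer VR may want its whole effect, expectation included. This also stands. A reader might infer that the t-test is biased or the trial invalid. The documents do not support that: the test is valid for the effect of assignment to VR on reported pain. Only the attribution fails.
- **The controller is part of the treatment.** Section 10.1 says of the VR arm: "They will utilize a single controller to explore an underwater safari park". A reader might infer that an occupied hand is a further confounder. But 9.2 defines immersive VR by the user's interaction with the environment, so the controller belongs to the intervention as defined. Controls need not hold one.
- **The numbers are assumed.** The size and direction of the shift have no source in the documents. The 17 mm is an SD of change in patients reporting a little more or a little less pain (11.5), not of post-procedure scores. The plan also asks for at least 13 mm before a difference counts as clinically significant (11.6), which a small shift would rarely reach. All of this stands. A reader might take 10–20% as the trial's false-positive rate, and it is not that.

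A reader might also infer that participants are told VR works. The documents do not show this. Section 10.1 mentions education on benefits and risks, 14.4 says only "The subjects in the experimental group will potentially benefit from this study via reduction in anxiety and pain control", and the consent pages are not available for review.

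**Conclusion.** The claim in 10.1 goes further than the design allows. The switched-off headset supports the statement that a difference is not simply blindfolding. It does not support the statement that the difference is due to VR itself, because expectation and disappointment remain in a comparison of unblinded participants who rate their own pain. This conclusion rests on 10.1, 11.1 and 13.1 and needs no numerical assumption.

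The size cannot be determined from the documents. Under an assumed 3 to 5 mm shift, an SD of 17 mm and no VR effect, p<0.05 would occur about 10–20% of the time with 30 per arm, and an observed difference of 13 mm or more about 1–3% of the time. For the same shift, a larger SD would lower the chance of p<0.05 and a smaller SD would raise it. The 13 mm threshold therefore gives real protection against a small shift, but less against a large one, and expectation could still add to a true effect.

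The primary comparison, test and sample size need no change on this account. The wording and recruitment script should be corrected before data collection, which 16.1 expects to last only 3 to 4 days.

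**What to change.** 1. **Limit the claim in 10.1.** Suggested text: *The switched-off headset controls for covering the eyes and wearing the device. Participants know their arm and rate their own pain, so the difference is the total effect of being given VR, including expectation.* Carry the same limit into the conclusions foreseen in 9.2 and 14.4. Cost: a few sentences and a more modest claim.
2. **Use one neutral script** at the kiosk, consent and tutorial, saying that it is not known whether either headset condition is less painful. This agrees with 9.2, which calls the benefit in adults unclear. Cost: a short text and brief staff instruction.
3. **Reconcile 10.1 and 13.1** on what the envelope contains, so that it is clear when the participant learns the arm. Cost: wording only.
4. **Optional:** add one expected-pain VAS line after the arm is known and before the needle, reported by arm as description only. It would not separate expectation from the VR effect and should not be a covariate. Cost: one extra mark per participant, possible slight priming and, if the arm is learned only in the lab room, a step there before the headset goes on.

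No extra participants or staff are needed.

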Given the lack of research on the use of VR with common procedures such as IV access in an adult population, it remains unclear whether the use of VR would be beneficial in this population, or if the benefits are limited only to pediatric patients. If the results of this study show significant improved pain and anxiety levels in adults, thus rejecting the null hypothesis (which is that there will be no significant difference in pain or anxiety with and without the use of virtual reality), it would be reasonable to initiate further research into the use of VR for other common procedures performed in the emergency department, laboratory, family practice, or in the military setting while deployed.

9.3 Objectives/Specific Aims/Research Questions:

Describe the purpose and objective(s) of the study, specific aims, and/or research questions/hypotheses

The study's primary outcome is to determine if the use of immersive virtual reality with the Oculus Go improves the patient's pain ratings and pain intensity levels when undergoing venipuncture during routine blood draws versus the standard practice. We will use the Visual Analogue Scale (VAS) for pain assessment after each blood draw.

The study's secondary outcome is to assess procedure related anxiety before and after each intervention, which will also be measured with the VAS. We will also use the Likert scale to measure participant satisfaction with the procedure and whether or not they would request the use of VR again if available.

9.4 Study Design:

Describe study design in one to two sentences (e.g., prospective, use of existing records/data /specimens, observational, cross-sectional, interventional, randomized, placebo-controlled, cohort, etc.). Specify the phase – Phase I, II, III, or IV – for FDA-regulated investigational drug research

This study is a prospective randomized controlled trial comparing the standard practice for venipuncture to the standard practice with the addition of Virtual Reality. In order to test our hypothesis, we will be conducting this study in the phlebotomy lab on patients aged 18-50 years old who are already undergoing venipuncture for routine lab testing.

The study will test the participant's acute pain level associated with the procedure, as well as testing their level of procedure-related anxiety before and after the procedure.

9.5 Target Population:

Describe the population to whom the study findings will be generalized

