---------------------	----------------	---------------	------------------	-----------------------

How likely would you be to request Virtual Reality if it were available for use for other painful or anxiety-inducing procedures?

5 Very Likely	4 Likely	3 Not Sure	2 Unlikely	1 Very Unlikely
------------------	-------------	---------------	---------------	--------------------

10.2 Data Collection:

Describe all the data variables, information to be collected, the source of the data, and how the data will be operationally measured.

The independent variable for this study is the use of VR or lack thereof. The dependent variables include accurately measuring anxiety levels pre and post procedure, pain levels after the procedure, and satisfaction with the procedure in regards to pain control, anxiety management, and ease of use. The participant's gender, age, and a minimal medical history will be obtained for purposes of inclusion or exclusion from the study. The information collected relevant to the conduct of the study will include any history of bloodborne disease, anxiety, seizures, pregnancy status, right vs left handedness, VR experience, nausea, vomiting, or vertigo. Participants will also be asked to rate their expected pain and anxiety associated with venipuncture using the Visual Analog Scale (VAS). The above information will be collected on the self-reported data sheet prior to providing specimens. The questionnaires will also enquire as to whether the participant took any pain medications prior to arrival, as well as rate pre and post-procedure anxiety level on a VAS scale. Finally, patients will then rate their procedure related pain intensity on the VAS scale.

Participants will also be asked about their satisfaction level with the use of VR in regards to pain control, anxiety management, and ease of use and their likelihood of requesting VR if available in the future using the Likert scale. All information will be provided and data collected voluntarily, and participants may choose not to answer any questions they choose.

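### Satisfaction with the procedure is a named descriptive outcome, but both printed satisfaction items ask about VR use, so they give no between-arm comparison of it

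*Combined protocol and SAP*

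**What the plan says.** Section 9.3 names procedure-related anxiety as the secondary outcome. In the same paragraph it adds that a Likert scale will be used "to measure participant satisfaction with the procedure and whether or not they would request the use of VR again if available". Section 10.2 lists among the dependent variables "satisfaction with the procedure in regards to pain control, anxiety management, and ease of use". Section 11.1 places satisfaction with the procedure among the additional outcomes and says the Likert results will be reported as they stand.

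Section 10.1 states that "each participant will be asked to fill out the post-procedure questionnaire", and that the questionnaire covers "satisfaction with the visit which will be measured utilizing a Likert scale for individual questions". Two satisfaction items are then printed: "Overall, how satisfied were you with the use of Virtual Reality in reducing your pain level" and "Overall, how satisfied were you with the use of Virtual Reality in reducing your anxiety level". A third item asks how likely the participant would be to request VR for other procedures. Section 11.1 reprints all three. Section 11.6 gives a shorter satisfaction item, which also refers only to the use of VR.

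On exposure, 10.1 says that "all participants will undergo a brief instructional class on how to operate the HMD" before allocation, for about 5 to 10 minutes. For the control arm during the draw it says: "Those not using the VR will still wear a headset that will simply be turned off". Section 11.4 plans 30 participants per arm.

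**The concern.** The outcome as named can be experienced in both arms, because everyone has a blood draw and can be more or less satisfied with it. The items as printed presuppose that VR was used to reduce pain or anxiety, which applies to one arm only. A control who answers has to guess what is meant: the tutorial, the dark headset, or VR in general. No not-applicable option, control-arm version or skip instruction is described.

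At stake is the trial's only descriptive evidence on patient experience. The title asks whether VR improves it, and section 9.6 argues that VR could raise satisfaction with a visit. If satisfaction is recorded only as an opinion of VR, the trial can say how VR users rated VR. It cannot say whether they were more satisfied with their blood draw than controls were. The gap could not be repaired afterwards: section 16.1 expects data collection to last 3 to 4 days, and section 13.6 says participants cannot be identified once the questionnaires are complete.

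**Working it through.** This is a comparison of the outcome with its measure, so most of the check is textual.

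1. **Outcome as named.** Satisfaction with the procedure: 9.3, 10.2 (dependent variables) and 11.1. Satisfaction with the visit: 10.1.

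2. **Outcome as measured.** Printed satisfaction items in 10.1 and 11.1: 2. Items that ask about VR use: 2 of 2. Items that ask about the draw, the procedure or the visit: 0 of 2. The short item in 11.6 is also about VR. Later text in 10.2 describes the measure as satisfaction with VR or with the headset, so 10.2 does not agree with itself on the construct.

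3. **Who answers.** All participants (10.1). Planned controls are 30 of 60, and 30/60 = 50%.

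4. **What controls can answer.**
   - Pain item: VR was off when the needle went in, and the tutorial involved no needle. There is no valid meaning.
   - Anxiety item: the tutorial came before the draw, so a control could perhaps rate its effect on anticipatory anxiety. That is a different question from the one VR users answer, so there is little valid meaning.
   - Request-VR item: it is hypothetical, and both arms can answer it. No problem.

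5. **A dimension with no item.** Section 10.2 lists ease of use as part of satisfaction, but no such item is printed. This is a second gap between outcome and items. It also shows that the printed list may not be the whole form.

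6. **Does the sample size depend on this?** Section 11.5 uses 13 mm and an SD of 17 mm for VAS pain, two-sided alpha 0.05 and power 0.80. By the normal approximation, n per arm = 2 × (1.960 + 0.842)² × 17² / 13² = 26.8, so 27, as the plan states. Allowing for dropout, 54 / (1 − 0.10) = 60, also as stated. (A t-based calculation gives 28 per arm, which is immaterial here.) No Likert quantity enters, so neither the sample size nor the primary test changes.

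**The case against.** The strongest reply is that these are VR-acceptability items under a loose label. Section 10.2 twice describes them that way, and 9.3 pairs satisfaction with requesting VR again, which suits people who have used it. Relabelling the outcome and limiting the items to the VR arm would make the text consistent. That is true, and it is the smallest possible repair. It would leave satisfaction with the procedure, named in three sections, without a measure, and the title's question about experience without a comparison. Controls would also have no reason to be asked these items.

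A second reply is that controls may answer "not sure" or skip. Section 10.2 does let anyone skip any question, but that is a general right and not an instruction to controls. A middle response from a control does not mean what it means from a VR user.

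Some stronger readings are tempting but not supported:

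- *The two arms' answers will be pooled, so controls will distort the VR ratings.* No section says so. Section 10.2 makes VR use or its absence the independent variable, and 11.1 commits to intention to treat. Both point to results by assigned arm.
- *The questionnaire has no item on the procedure at all.* The form itself is not in the documents, and the missing ease-of-use item shows that the printed list may be incomplete.
- *A main secondary outcome is lost.* Section 9.3 gives that place to anxiety, and 11.1 calls satisfaction additional.
- *Controls have no experience of VR.* They have the tutorial.

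**Conclusion.** The point holds as a mismatch between a named outcome and its printed measure. Both printed satisfaction items are tied to VR use. For the 30 controls the pain item has no valid meaning and the anxiety item has little, so the printed items give no between-arm comparison of satisfaction with the procedure. The ease-of-use dimension has no printed item in either arm.

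The consequence is limited to one additional, descriptive outcome. No hypothesis, test or sample size rests on it, and VR users' ratings of VR remain interpretable when shown for that arm. The conclusion assumes that the items printed in 10.1 and 11.1 are those on the form. If the form already carries an arm-neutral satisfaction item, what remains is to bring the protocol text into line with it. The change is worth making before enrolment because it is cheap then and impossible later.

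**What to change.** Before enrolment, make the same change in sections 10.1, 10.2, 11.1 and 11.6:

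1. Add arm-neutral items that everyone can answer, for example *Overall, how satisfied were you with this blood draw?*, and the same for how pain and how anxiety were managed during the draw. Report them descriptively by arm.
2. Keep the VR-satisfaction items, with an ease-of-use item if that dimension is retained. Give each the option *Not applicable: VR not used during my blood draw*, and report them for the VR arm only.
3. Keep the request-VR item for both arms and report it by arm.
4. Use the same names in all four sections: satisfaction with the procedure for the arm-neutral items, and satisfaction with VR for the VR items. Section 9.3 can then stand as written.

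The cost is three short items (four with ease of use), one extra response option and matching sentences in four sections. The form becomes slightly longer. No extra participants, visits or tests are needed.
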